## **Abstract**

Our planned study aims to evaluate the efficacy of transcutaneous electrical nerve stimulation for analgesia at the time of outpatient endometrial biopsy.

We will conduct a double-blind, placebo-controlled randomized controlled trial. We will recruit patients over 18 years of age who are undergoing an outpatient endometrial biopsy at Duke gynecologic oncology and general gynecology clinics. After informed consent, participants will be randomized to either the active TENS arm or the placebo TENS arm. They will obtain a pre-procedural survey to collect demographic and personal information as well as a post-procedural survey to assess for post-procedural symptoms, acceptability and tolerability. Pain at the time of endometrial biopsy will be collected across discrete time intervals using a visual analogue scale (VAS).

We hope to recruit 160 participants for this trial and we plan to analyze pain scores between the control and treatment groups as our primary study objective. Risks will be minimal given that TENS is accepted as a safe, over-the-counter non-pharmacologic analgesia method.

## **Design and Procedures**

### Patient selection

We will conduct a double-blind, placebo-controlled randomized controlled trial. We will recruit patients over 18 years of age who are undergoing an outpatient endometrial biopsy at Duke gynecologic oncology and general gynecology clinics. Our exclusion criteria include age younger than 18 years, unable to follow study instructions and/or independently adjust TENS settings, cutaneous damage at the TENS application site, any electronic implanted device, inability to understand or declines to sign the informed consent form, and previous personal experience using a TENS unit. We also will not enroll patients who are undergoing a concurrent procedure at the time of biopsy (ie. they're having a biopsy and an IUD placed). Pregnant women will be excluded from the study as a part of the standard of care before having an endometrial biopsy, therefore a pregnancy test may be done for reproductive-aged women. Endometrial biopsy is used to detect endometrial hyperplasia and cancer, however we expect fewer than 15% of patients to be diagnosed with endometrial cancer.

### Spanish-speaking Participants Long form translation

The study consent form has been translated into Spanish by Communication Access Partners, Inc DBA Language Resources, a translation company based in Greensboro, NC. The Spanish version of the long consent form can be found in the consent form section of this protocol. The back translation (Spanish into English) and translation certificates can be found in the Other Protocol Documents section. The certified medical Spanish interpreter in clinic will present the consent form to the patient with a study team member present. They will translate any questions the patient has for the study team member into English, and then they will translate the study team responses back into Spanish for the patient. If the patient agrees to participate, they will sign the consent form as will the study team member. The study team member will document the translator's name and that the Spanish version of the consent

was presented to the patient by the translator in the consent documentation note in Epic. Spanish-speaking patients will have survey questions interpreted by the medical Spanish interpreter; our surveys will not be interpreted into Spanish prior. The interpreter will interpret and accompany Spanish-speaking patients throughout the entire procedure.

#### Short form translation

Spanish-speaking patients may also be included using a certified medical Spanish interpreter and a bilingual adult witness using a short-form Spanish consent. Spanish-speaking patients will have survey questions interpreted by the medical Spanish interpreter; our surveys will not be interpreted into Spanish prior. The interpreter will interpret and accompany Spanish-speaking patients throughout the entire procedure. The bilingual adult witness may be a clinician, if needed. The clinician will not be affiliated with this study and will not be on KP.

Given that many endometrial biopsies will be determined as part of the workup during a visit for abnormal uterine bleeding, eligible patients will be introduced the study at the time of determination for an endometrial biopsy. Participants will have the entirety of time from introduction of study to starting the procedure to decide whether to enroll, and can withdraw from the study at any time.

After informed consent, participants will be randomized to either the active TENS arm or the placebo TENS arm. Randomization will occur in Redcap using a schema provided by the statistician. Participant demographics and clinical information will be collected on a standardized survey in RedCap including self-reported age, race, ethnicity, level of education, history of previous endometrial biopsy, medical history, daily narcotic, or anxiolytic use. Pre-procedural anxiety will be assessed via a 100 mm visual analogue scale with 0 mm being “no anxiety at all” and 100 being “the most anxious I have ever been”.

As there is no standard analgesia option, patients may be offered pain medication prior to the procedure such as ibuprofen. While this would not be a contraindication to enrollment, we anticipate adequate block randomization for this to normalize in both groups, and we will note what form of analgesia was used during our statistical analysis. We believe there is an important value to allow providers to continue their normal standard of care options.

#### Intervention

Participants will be randomly assigned either to the active TENS group or the placebo TENS group via the Redcap randomization tool. We will attempt to blind both the patient and the provider to the intervention. The clinical research coordinator helping with placement, teaching, and operation of the TENS unit will not be blinded. Clinical coordinators will read from a prepared script that will be the same for the placebo and intervention arms. A Spanish-speaking patient will have the script interpreted to them by a certified medical Spanish interpreter. A TENS 7000 that is FDA-approved will be used for this project. TENS units will be placed parallel to the vertebral column at the T-10-L1 and S2-S4 levels as done in previous studies.

Prior to applying the TENS pads to the patient, the study coordinators will ensure the TENS unit has been set to the determined, standardized frequency. The patient will be able to adjust the intensity.

All subjects will have four TENS pads placed on their backs. Those in the active TENS group will have all four electrodes connected to all four pads by the study coordinator. Those in placebo TENS group will have

only two electrodes (one electrode from each wire) connected to two pads. The remaining two electrodes (one from each wire) will be covered with a tight-fitting cap. The subjects can still turn on and adjust the device, just as they would if they were in the active TENS group.

The TENS will be initially turned onto a low frequency by the clinical coordinator. This will be standardized for all patients. The patient will then be told to individually adjust the intensity to each patient's maximum sensory level, or when they feel a strong tingling sensation that is not painful. Patients will be told to maintain the stimulation at the maximum non-painful level and to increase the intensity if they are experiencing pain during the procedure. The TENS will start 5 minutes prior to the procedure and continue until 5 minutes after the completion of the procedure. The provider will be blinded to the patients' group allocations as they will enter the room after initiation of TENS.

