#### Outcome Measures

The primary outcome will be pain at the time of endometrial biopsy; we hypothesize that participants in the active TENS group will have reduced pain scores compared to placebo group. Pain scores will be collected using a 0-100 mm visual analogue scale (VAS) with 0 mm being "no pain" and 100 mm being "worst pain imaginable" during the procedure to be collected by the clinical coordinator. VAS scores will also be collected at the following discrete times: speculum placement, tenaculum placement, immediately after biopsy, removal of speculum, 5 minutes after biopsy and 15 minutes after biopsy.

Patients and providers will fill out a post-evaluation survey including post-procedural symptoms and questions to assess tolerability and acceptability of the biopsy procedure. Secondary outcomes include pain scores at other intervals throughout the procedure, satisfaction with the biopsy, and whether certain factors (anxiety level at the time of biopsy, medication use, sociodemographic factors) are correlated with higher pain scores. Patients will also be asked if they thought they were in the placebo group or the treatment group, and whether they would choose the same pain control if they had to have another EMB. Providers will be asked to evaluate ease of procedure on a 100 mm scale and to estimate perceived pain during the procedure on a 100 mm VAS scale. All information will be collected in RedCap.

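### Does the half-connected placebo, with no stated analysis of patients' treatment guesses, call for a change to the plan?

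*Protocol*

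**What the plan says.** The protocol's Abstract calls the trial double-blind. Its Intervention section states the aim more cautiously: "We will attempt to blind both the patient and the provider to the intervention".

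- **Placebo set-up (Intervention).** All patients wear four pads. The placebo arm has "only two electrodes (one electrode from each wire) connected to two pads", and "The remaining two electrodes (one from each wire) will be covered with a tight-fitting cap". Placebo patients can still switch the unit on and adjust it.
- **Instruction (Intervention).** Patients in both arms turn the intensity up to the point "when they feel a strong tingling sensation that is not painful", and further if the procedure hurts.
- **Staff (Intervention).** "The clinical research coordinator helping with placement, teaching, and operation of the TENS unit will not be blinded". Coordinators read one prepared script, identical in both arms. The provider enters only after the unit has been started.
- **Eligibility (Patient selection).** Patients with "previous personal experience using a TENS unit" are excluded.
- **Check on blinding (Outcome Measures).** "Patients will also be asked if they thought they were in the placebo group or the treatment group". This is described alongside the post-procedure survey, and "All information will be collected in RedCap".
- **SAP.** The primary outcome is the VAS immediately after biopsy, compared by linear regression adjusted for baseline pain. The treatment guess is not mentioned, either in the primary model or among the secondary outcomes.

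**The concern.** The instruction tells patients what an active unit should feel like. If capping one electrode of each wire leaves the circuit open, a placebo patient could turn the dial up, feel nothing and draw the obvious conclusion. The unblinded coordinator is a second possible route, and the Outcome Measures section has the clinical coordinator collect the pain scores.

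A self-reported pain score is open to expectation. If the arms differ in how many patients believe they had active TENS, part of the difference in VAS could come from that belief.

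The treatment guess is the only check on patient blinding that the documents describe. It appears to be asked after the biopsy, so a correct guess could come from sensation or from having felt less pain. With no reading agreed beforehand, a table of guesses could be misread either way: effective treatment taken for unblinding, or unblinding explained away as effective treatment.

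**Working it through.** **The plan's own figure.** Inputs from the SAP: difference 15 mm, SD 30 mm (d = 15/30 = 0.5), two-sided alpha 0.05, power 80%. A two-sample t-test needs 63.8, so 64 per arm (power 0.801). Allowing for 20% attrition, 128/0.8 = 160. The sample size reproduces and is not in dispute.

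**How much expectation would matter.** At 64 per arm:
- SE = 30 × √(2/64) = 5.30 mm.
- 95% half-width = 1.979 × 5.30 = 10.5 mm.
- An observed 15 mm difference loses significance if 15 − 10.5 = 4.5 mm of it is bias. At 80 per arm the half-width is 9.37 mm and the margin 5.63 mm.

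This margin holds for any source of bias in any trial of this size. It says nothing about this placebo in particular.

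**Illustration on assumed inputs.** The documents give no size for an expectation effect. Take bias = (difference between arms in the share believing they had active TENS) × (assumed VAS shift from that belief), with no true effect and 64 per arm:

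| Belief gap | Assumed shift | Bias | Chance of p < 0.05 |
|---|---|---|---|
| 20% | 5 mm | 1 mm | 5.4% |
| 40% | 10 mm | 4 mm | 11.6% |
| 60% | 10 mm | 6 mm | 20.2% |
| 80% | 15 mm | 12 mm | 61.2% |

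The range is wide because both inputs are unknown. It shows what would be at stake, not what is likely.

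**What a table of guesses can show.** Suppose blinding holds, TENS works as planned and patients guess only from biopsy pain. For normal VAS scores with equal SDs, the largest possible difference between arms in the share guessing active is 2Φ(d/2) − 1. At d = 0.5 this is 2 × 0.599 − 1 = 0.197, that is 59.9% against 40.1%. Bounded 0–100 distributions (SD 30 mm, assumed placebo means of 50 to 70 mm) give 0.199 to 0.236.

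When both shares are near one half, the 95% half-width for the difference is 1.96 × √(2 × 0.25/64) = 0.17 at 64 per arm. By exact enumeration with Newcombe intervals, 59.9% against 40.1% gives a lower limit above zero in about 60% of trials. A difference from zero is therefore the usual result in a sound trial of an effective treatment.

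**Whether a pre-set threshold would help.** One candidate rule infers unblinding only when the lower limit exceeds 0.20, raising that limit to 2Φ(d/2) − 1 if the observed d is above 0.5. At 64 per arm:

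| True shares guessing active (active v placebo) | Lower limit > 0.20 |
|---|---|
| 59.9% v 40.1% (pain relief only) | 2.4% |
| 65% v 35% | 21% |
| 70% v 30% | 66% |
| 75% v 25% | 96% |

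The rule has four weaknesses:
- If expectation inflates the observed effect, the limit rises with it. At an observed 20 mm the limit is 0.26, and detection at 70% v 30% falls from 66% to 36%.
- The limit never drops below 0.20, even when the observed effect is near zero and pain relief could not explain a difference in guesses.
- It lies below 0.236, the upper end of the bounded calculation.
- Between 0 and 0.20 it can only say that the two explanations cannot be told apart, which is where matters stand without it.

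**The case for a change.** The strongest case for a change is that it would cost one paragraph and one table from data already held, leave patients and the primary analysis alone, and settle before the results are known whether the trial may be called double-blind without qualification. The identical script does not remove the cue, because it is the instruction itself that names the sensation. A threshold of 0.20 would rarely fire wrongly (2.4%) and would catch gross unblinding (96% at 75% v 25%).

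Part of this stands. The SAP is silent on the guess, blinding could be imperfect, and a table of guesses read carelessly can mislead. The case for amending does not. That placebo patients feel nothing is inferred from the wiring; the circuit details, script and consent wording are not available to read. The favourable rates for the threshold apply only while the observed d is at most 0.5, which a true 15 mm effect would exceed about half the time. No analysis of a single guess that appears to be taken after the procedure can recover the distinction that the concern asks for.

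**Conclusion.** No change to the plan follows. The risk to patient blinding is possible but not established, and the plan already limits it through the common script, TENS-naive patients, four pads in both arms, an adjustable unit and a provider who enters after start-up. The relevant information is collected. What is unwritten is how to describe one secondary table, and ordinary practice covers that: guesses by arm, the difference in the share guessing active with its 95% interval, any don't-know answers shown separately, and a statement that a difference may reflect unblinding or felt pain relief.

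The primary estimate, its test and the 160 recruited are the same with or without that text. The 4.5 mm margin (5.6 mm at 80 per arm) is generic and assumes an observed 15 mm difference, SD 30 mm and no gain in precision from the covariate. The 0.20 figure assumes guesses rest on biopsy pain alone; guesses that draw on several pain scores could exceed it. The conclusion depends on neither figure: a reading rule would add no information that separates the two explanations.

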#### Outcome Measures

The primary outcome will be pain at the time of endometrial biopsy; we hypothesize that participants in the active TENS group will have reduced pain scores compared to placebo group. Pain scores will be collected using a 0-100 mm visual analogue scale (VAS) with 0 mm being "no pain" and 100 mm being "worst pain imaginable" during the procedure to be collected by the clinical coordinator. VAS scores will also be collected at the following discrete times: speculum placement, tenaculum placement, immediately after biopsy, removal of speculum, 5 minutes after biopsy and 15 minutes after biopsy.

Patients and providers will fill out a post-evaluation survey including post-procedural symptoms and questions to assess tolerability and acceptability of the biopsy procedure. Secondary outcomes include pain scores at other intervals throughout the procedure, satisfaction with the biopsy, and whether certain factors (anxiety level at the time of biopsy, medication use, sociodemographic factors) are correlated with higher pain scores. Patients will also be asked if they thought they were in the placebo group or the treatment group, and whether they would choose the same pain control if they had to have another EMB. Providers will be asked to evaluate ease of procedure on a 100 mm scale and to estimate perceived pain during the procedure on a 100 mm VAS scale. All information will be collected in RedCap.

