IRB Number: Pro00111100

NCT05472740

Study Title: Transcutaneous electric nerve stimulation for analgesia during outpatient endometrial biopsy: a randomized controlled trial (TENS RCT)

PI: [name]

Study Location: Duke University

V1.9 Approval Date: 08/23/2023

We plan to conduct a superiority trial. Prior research has established that a 25-30% reduction in overall pain or a 13-15 mm decrease in VAS represent clinically significant differences in pain scores. We determined a standard deviation of 30 mm as based on a prior similar study by Yilmazer et al. We will conservatively plan for a sample size sufficient to detect a 15 mm reduction in pain scores in the intervention group as compared to the control group. We would need 64 subjects in each group for a total of 128 subjects to attain 80% power at alpha = 0.05 level of significance, which corresponds to a Cohen's d around 0.50 (moderate reduction). We hope to recruit 160 participants for this trial to account for an assumed attrition rate of 20%.

Data will be recorded using Research Electronic Data Capture (REDCap). Pain will be measured along discrete intervals including: speculum placement, tenaculum placement, immediately after biopsy, removal of speculum, 5 minutes after biopsy and 15 minutes after biopsy. The primary outcome will be pain score immediately after biopsy. The primary outcome will be compared between treatment arms using linear regression adjusting for baseline pain. Secondary outcomes include pain score at other intervals, patient tolerability and acceptability, and provider's satisfaction with the procedure. All testing will be performed at a two-tailed significance level of 0.05.

As there is no standard analgesia option, patients may be offered pain medication prior to the procedure such as ibuprofen. While this would not be a contraindication to enrollment, we anticipate adequate block randomization for this to normalize in both groups, and we will note what form of analgesia was used during our statistical analysis. We believe there is an important value to allow providers to continue their normal standard of care options.

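### Does the protocol leave the primary pain score undefined, when only the SAP names the VAS taken immediately after biopsy?

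*Protocol*

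**What the plan says.** **Protocol, Outcome Measures.** The primary outcome is introduced with "The primary outcome will be pain at the time of endometrial biopsy". The next sentence gives the instrument (a 0-100 mm VAS), its anchors and who records it: "during the procedure to be collected by the clinical coordinator". The times follow: "VAS scores will also be collected at the following discrete times: speculum placement, tenaculum placement, immediately after biopsy", then speculum removal and 5 and 15 minutes after biopsy. The secondary list reads "Secondary outcomes include pain scores at other intervals throughout the procedure". The provider also gives a rating and is asked "to estimate perceived pain during the procedure on a 100 mm VAS scale".

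**Protocol, Abstract.** The same phrase is applied to the whole series: "Pain at the time of endometrial biopsy will be collected across discrete time intervals using a visual analogue scale (VAS".

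**SAP, second paragraph.** "Pain will be measured along discrete intervals including: speculum placement, tenaculum placement, immediately after biopsy, removal of speculum", followed by the same two later times. Then: "The primary outcome will be pain score immediately after biopsy". The comparison between arms is a linear regression adjusted for baseline pain, and all tests are two-sided at 0.05. Pain at the other intervals is secondary here too.

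**The concern.** Three features of the text make this look like a defect.

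- The protocol states a concept, biopsy pain, and never says which score measures it. The Abstract uses the same words for several scores.
- Outcome Measures first mentions scores taken during the procedure and then says that scores will *also* be taken at six times. Taken literally, the score immediately after biopsy is additional to some other score that might be the primary one. The SAP lists no such score.
- Neither document says whether the VAS immediately after biopsy asks about the pain of the biopsy or the pain felt at that moment. The provider's rating does have a stated reference period.

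If the choice were open, an analyst could pick the primary score after seeing the data. The nominal 5% error rate would then not hold, and the score tested might not be the one the hypothesis concerns.

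**Working it through.** **1. The plan's own figure.** Inputs from the SAP, first paragraph: difference 15 mm, SD 30 mm, alpha 0.05, power 80%, attrition 20%. The two-sided level is in the second paragraph.

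- Standardised difference: 15 / 30 = 0.50.
- Normal approximation: n = 2(1.960 + 0.842)² / 0.50² = 62.8, so 63 per group.
- Two-sample t-test: 63.8, so 64 per group. Power at 64 is 80.1%.
- Attrition: 128 / (1 − 0.20) = 160, and 160 × 0.80 = 128.

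The stated 64, 128 and 160 reproduce. Nothing in this calculation depends on which VAS time is called primary, provided the 15 mm and 30 mm apply to that score.

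**2. The times side by side.**

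| VAS time | Protocol | SAP | Relation to the biopsy |
|---|---|---|---|
| Speculum placement | listed | listed | before |
| Tenaculum placement | listed | listed | before |
| Immediately after biopsy | listed | listed, **primary** | directly follows |
| Speculum removal | listed | listed | a separate step |
| 5 minutes after | listed | listed | later |
| 15 minutes after | listed | listed | later |

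Both documents list the same six times. With one primary, 6 − 1 = 5 are secondary.

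**3. Is there a seventh score?** The protocol's secondary pain outcomes are scores at *other* intervals. That wording makes sense only if the primary score belongs to one of the intervals. The sentence about collection during the procedure is most simply read as describing the instrument and the collector, with the times following. Of the six times, only the one immediately after biopsy fits the phrase in "The primary outcome will be pain at the time of endometrial biopsy". The SAP makes the same choice explicitly.

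**4. What an open choice would cost.** Suppose either of two scores could be declared primary at 0.05. If they were independent, the false-positive rate would be 1 − 0.95² = 9.75%. In a simulation of correlated test statistics it is about 9.1%, 8.4% and 7.0% at correlations of 0.5, 0.7 and 0.9. These correlations are assumptions, since the documents give none. The inflation needs an open choice, and the SAP names one score, so it does not arise.

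**The case for a change.** The strongest opposing case is that the SAP fixes when the score is taken but not what it asks. Pain recalled from the biopsy and pain felt a moment later can differ, and the hypothesis concerns the former. Consistent wording matters in this trial. The coordinator who operates the TENS unit is unblinded (Protocol, Intervention), a clinical coordinator collects the scores, and survey questions for Spanish-speaking patients are interpreted live.

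Part of this stands. The reference period is not in the text, and the protocol would read better if it named the score and dropped *also*. But the REDCap forms and the coordinator's VAS wording are not among the documents, so their silence does not show that the prompt lacks a reference period. The contrast with the provider's rating is weak: that is one overall rating and needs a period, whereas each patient score is attached to a named moment.

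Rewording the prompt could also do harm. The SAP carries an approval date of 08/23/2023, and the protocol's Study Duration section expected enrolment to stop in October 2023 or at 160 consents. A new prompt that late could mix two measurements within the primary outcome. Reporting the prompt actually used is ordinary good practice and needs no change to the plan.

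A reader might also say that the protocol should stand alone. The SAP exists to turn a protocol's outcome concept into a specific score, and here it does so without contradicting any primary time point named in the protocol.

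**Conclusion.** No change to the plan follows. The quoted wording is loose, but the two documents together identify one primary score, the VAS immediately after biopsy, with its method and significance level set in advance. An analyst following the plan would reach that score without a judgement call. Sample size, power and false-positive rate are unaffected. Harmonising the protocol's wording would be editorial and would alter no result.

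This rests on two assumptions: that the SAP governs the primary analysis, and that any separate score taken during the procedure, if one exists, is not used in place of the named one. The reference period of the VAS prompt remains unknown from these documents. It is missing detail, and no error in the plan has been shown.
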